#### And at least one of the following:

- a) fever (>38°C) with no other recognized cause
- b) leucopenia (12,000 cells/mm^3)
- c). for adults >70 years old, altered mental status with no other recognized cause

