# 5.4. Secondary clinical outcome measures

- DAH30 is a continuous number between 0 and 30, reflecting the total number
  of days that a patient spends alive and at home within 30 days after surgery.
  In this definition, home reflects any place other than hospital. If a patient dies
  within those 30 days, their value is set to 0. DAH30 captures the development
  of all-cause complications which prevents patients leaving hospital after
  surgery.
- Increase in serum high sensitivity troponin-T (Elecsys, Roche Diagnostics)
   concentration of:
  - a. An absolute value of ≥15ng L on day one after surgery
     OR
  - b. An increase of  $\geq 5$  ng L from the preoperative value on day one after surgery when the preoperative value of  $\geq 15$ ng L
- Incidence of postoperative infection within 30 days after surgery. This is defined as one or more of the following infections of Clavien-Dindo grade II or greater. A full list of definitions is available in Appendix A:
  - a. Superficial surgical site infection;
  - b. Deep surgical site infection;
  - c. Organ space surgical site infection;
  - d. Pneumonia;
  - e. Urinary tract infection;
  - f. Laboratory confirmed blood stream infection;
  - g. Infection, source uncertain; this is defined as an infection which could be more than one of the above (i.e. a-f), but it is unclear which.
- Continuous glucose measurements using continuous glucose monitoring (CGM) up to 10 days after surgery or hospital discharge whichever is sooner.

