#### Urinary tract infection

A positive urine culture of ≥105 colony forming units/mL with no more than two species of micro-organisms with at least one of the following symptoms or signs: fever (>38 °C), urgency, frequency, dysuria, supra-pubic tenderness, costo-vertebral angle pain or tenderness with no other recognised cause, identified within a 24-hour period.

Alternatively, the patient has an abscess or other evidence of infection seen on direct examination, during a surgical operation, or during a histopathologic examination with one of the following:

- a) purulent drainage from affected site;
- b) radiographic evidence of infection;

c) physician diagnosis of infection of the kidney, ureter, bladder, urethra, or tissues surrounding the retroperitoneal or perinephric space; d) physician institutes antibiotic therapy for an infection of the kidney, ureter, bladder, urethra, or surrounding tissues.

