#### Laboratory confirmed bloodstream infection

An infection which meets at least one of the following criteria but is not related to infection at another site:

- Patient has a recognised pathogen cultured from one or more blood cultures and the organism cultured from blood is not related to an infection at another site
- Patient has at least one of the following signs or symptoms: fever (>38°C), chills, or hypotension and at least one of the following:
  - a) common skin contaminant cultured from two or more blood cultures drawn on separate occasions
  - b) common skin contaminant cultured from at least one blood culture from a patient with an intravascular line, and the physician institutes antimicrobial therapy
  - c) positive blood antigen test

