#### Infection, source uncertain

An infection which is considered likely to be one of the following but cannot be differentiated because clinical information suggests more than one possible site: Superficial surgical site infection, or Deep surgical site infection, or Organ space surgical site infection, or Pneumonia, or Urinary tract infection, or Laboratory confirmed blood stream infection. There must be a strong clinical suspicion of infection meeting two or more of the following criteria:

- 1. Core temperature 38°C
- 2. White cell count >12 x  $10^9$ /L or <4 x  $10^9$ /L
- 3. Respiratory rate >20 breaths per minute or PaCO2 <35 mmHg
- 4. Pulse rate >90 beats per minute

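### The Appendix A pneumonia definition ties leucopenia to the appendix's own high white-cell limit and gives no leucocytosis criterion

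*Protocol*

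**What the plan says.** Section 5.4 lists infection within 30 days as a secondary clinical outcome, with pneumonia among its components, and states: "A full list of definitions is available in Appendix A".

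In Appendix A, pneumonia needs radiographic change, at least one sign from a list of three, and at least two respiratory features. The three signs are:

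- a) "fever (>38°C) with no other recognized cause"
- b) "leucopenia (12,000 cells/mm" (cubed)
- c) altered mental status, for adults over 70 only

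For infection of uncertain source the appendix says: "There must be a strong clinical suspicion of infection meeting two or more of the following criteria". The four criteria include "Core temperature 38°C", and a white-cell item that begins "White cell count >12 x" 10^9/L and gives below 4 x 10^9/L as the alternative.

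Under section 7.7 a research associate makes the first assessment. A negative call stands as the outcome; only a positive call goes to the site Principal Investigator. Section 13.6 says the study team will not routinely monitor data collection at hospitals or verify source data.

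**The concern.** Leucopenia means a low white-cell count, and 12,000 cells/mm3 is not a low count by the appendix's own limits. The item has no direction sign, and leucocytosis appears nowhere in the pneumonia definition. An assessor following the text has no usable white-cell threshold.

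Sites classify events from this appendix, so the wording itself decides who counts as an event. If sites resolve the item differently, or apply it literally, some pneumonias will be missed. Because negative calls are not reviewed, such errors would not come back for correction. Misclassification unrelated to arm pulls a difference between arms toward zero.

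**Working it through.** **1. Units.** 1 L = 10^6 mm3.

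- 12,000 cells/mm3 x 10^6 = 12 x 10^9/L
- 4 x 10^9/L / 10^6 = 4,000 cells/mm3

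The printed pneumonia value equals the high limit used under infection of uncertain source, and is 12,000 / 4,000 = 3 times the low limit.

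**2. The items side by side (all from Appendix A).**

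| Definition | White-cell item | Temperature item |
|---|---|---|
| Pneumonia | "leucopenia (12,000 cells/mm" (cubed); no sign, no high-count term | "fever (>38°C) with no other recognized cause" |
| Uncertain source | above 12 or below 4 x 10^9/L | "Core temperature 38°C"; no sign |
| Urinary tract | none | "fever (>38 °C), urgency, frequency, dysuria" |
| Bloodstream | none | "fever (>38°C), chills, or hypotension" |
| Deep surgical site | none | fever above 38°C |

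The white-cell items disagree. The temperature items share one number, and only the uncertain-source line lacks its direction.

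**3. Which patients the pneumonia item affects.** The sign list is mandatory. The altered-mental-status route is open only above age 70, and section 6.2 admits patients from age 50. For ages 50 to 70 two routes remain: fever, or item b). Take an afebrile 65-year-old with consolidation, purulent sputum, hypoxia and a count of 18,000 cells/mm3. Radiography and respiratory features are met. Fever is absent, a count of 18,000 is not leucopenia, and the age route is closed. The patient fails the definition. The uncertain-source category does not rescue the case, because it is reserved for infections that could lie at more than one site.

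**4. What happens next.** The research associate records no infection. Section 7.7 makes that the outcome, with no referral to the Principal Investigator.

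**5. Sample size.** Section 10.1 powers a composite of myocardial injury and/or infection at 56% versus 40%, 90% power, 5% two-sided, 4% dropout, 450 patients. With mean proportion 0.48:

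- n per arm = [1.960 x sqrt(2 x 0.48 x 0.52) + 1.282 x sqrt(0.56 x 0.44 + 0.40 x 0.60)]^2 / 0.16^2 = 203 after rounding up
- with continuity correction, (203/4) x [1 + sqrt(1 + 4/(203 x 0.16))]^2 = 216 after rounding up
- total 2 x 216 = 432; 432 / 0.96 = 450

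The stated 450 is reproduced, and no diagnostic threshold enters the formula.

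**6. What can be sized.** Section 10.1 puts infection at about 20%, so 450 x 0.20 = 90 patients. The protocol gives neither the share of these that are pneumonia nor the share of pneumonias that would qualify only through a raised count. The number affected cannot be calculated from it.

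**The case against.** The strongest objection is that text was lost in reading the PDF. If the source read as leucopenia below one limit or leucocytosis above 12,000, deleting everything between a less-than sign and the next greater-than sign would leave exactly the printed string. The same loss would turn a two-sided temperature criterion into the bare 38°C. That source wording is an assumption. On the other side, section 4.1 keeps a less-than sign (glucose below 10 mmol/L) ahead of later markup on its line, the pneumonia item keeps its superscript, and the uncertain-source white-cell item keeps both signs. The available text therefore does not show that conversion removed the words, but it cannot exclude it. If the original PDF reads correctly, the point falls away. This part of the objection stands, and is why the first step is to check the PDF.

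It is also fair to say that experienced assessors may infer the intended meaning, and that item b) is only one of three alternatives.

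A reader might infer that sites will take the item as any count below 12,000 and so accept normal counts. That is strained: the word leucopenia rules out a normal count, and a positive call must be confirmed by the Principal Investigator.

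A reader might also attach an event count. Assuming 20-40% of the 90 infections are pneumonia (18-36) and 10-40% of those qualify only through leucocytosis gives about 2-14 lost infections. Neither share comes from the protocol, and the count is of infections, not composite events. Section 10.1 puts myocardial injury at about 48%, and those patients remain composite events. If the components were independent (a further assumption), 52% of 2-14 is about 1-7 lost composite events. Against 450 x 0.48 = 216 planned, that is roughly 0.4-3.5%, or at most about 0.6 points of the 16-point difference. This shows why the effect is probably small; it is not an estimate.

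**Conclusion.** The pneumonia white-cell item, as printed, cannot be applied and disagrees with the white-cell limits elsewhere in the same appendix. Its literal effect is to exclude afebrile pneumonia with a raised count in patients aged 70 or under, through an assessment path that does not revisit negative calls.

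A reader might infer that the infection endpoint's thresholds are wrong in general, or that the temperature item is a second contradiction. The documents support neither. Two items are affected, and 38°C agrees with every other fever criterion; it lacks only a sign.

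Nor is the trial's main inference touched. The primary outcome is blood glucose, infection is secondary, and no sample-size or power figure moves. The conclusion assumes that the original PDF carries the same wording. On that basis it is a small but real defect in an outcome definition, worth correcting because correction is cheap.

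**What to change.** 1. Check item b) of the pneumonia sign list against the original PDF and the sponsor's source definition. If the wording is as printed, reconcile it with the uncertain-source white-cell item so that low and high counts are both stated with inequalities. That item already gives below 4 and above 12 x 10^9/L.
2. As a minor clean-up, restore the missing inequality in the uncertain-source temperature item, again from the source definition.
3. Send the corrected appendix to sites before further events are classified.
4. If chest events already assessed are rechecked, include those called no infection, since these are the ones the wording would miss. The protocol does not state that site assessors are blinded, so the recheck should be done without knowledge of arm where possible, to avoid adding bias.

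The cost is one appendix correction, a note to sites and, if the recheck is done, a review of chest events from existing records. No new data are needed.

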#### And at least two of the following:

- a) new onset of purulent sputum or change in character of sputum, or increased respiratory secretions, or increased suctioning requirements
- b) new onset or worsening cough, or dyspnoea, or tachypnoea
- c) rales or bronchial breath sounds
- d) worsening gas exchange (hypoxia, increased oxygen requirement, increased ventilator demand)

#### Urinary tract infection

A positive urine culture of ≥105 colony forming units/mL with no more than two species of micro-organisms with at least one of the following symptoms or signs: fever (>38 °C), urgency, frequency, dysuria, supra-pubic tenderness, costo-vertebral angle pain or tenderness with no other recognised cause, identified within a 24-hour period.

Alternatively, the patient has an abscess or other evidence of infection seen on direct examination, during a surgical operation, or during a histopathologic examination with one of the following:

- a) purulent drainage from affected site;
- b) radiographic evidence of infection;

c) physician diagnosis of infection of the kidney, ureter, bladder, urethra, or tissues surrounding the retroperitoneal or perinephric space; d) physician institutes antibiotic therapy for an infection of the kidney, ureter, bladder, urethra, or surrounding tissues.

#### Laboratory confirmed bloodstream infection

An infection which meets at least one of the following criteria but is not related to infection at another site:

- Patient has a recognised pathogen cultured from one or more blood cultures and the organism cultured from blood is not related to an infection at another site
- Patient has at least one of the following signs or symptoms: fever (>38°C), chills, or hypotension and at least one of the following:
  - a) common skin contaminant cultured from two or more blood cultures drawn on separate occasions
  - b) common skin contaminant cultured from at least one blood culture from a patient with an intravascular line, and the physician institutes antimicrobial therapy
  - c) positive blood antigen test

#### Infection, source uncertain

An infection which is considered likely to be one of the following but cannot be differentiated because clinical information suggests more than one possible site: Superficial surgical site infection, or Deep surgical site infection, or Organ space surgical site infection, or Pneumonia, or Urinary tract infection, or Laboratory confirmed blood stream infection. There must be a strong clinical suspicion of infection meeting two or more of the following criteria:

- 1. Core temperature 38°C
- 2. White cell count >12 x  $10^9$ /L or <4 x  $10^9$ /L
- 3. Respiratory rate >20 breaths per minute or PaCO2 <35 mmHg
- 4. Pulse rate >90 beats per minute
